# 4.4 Exclusion Criteria

Patients will be excluded from the study if they meet any of the following criteria:

- Diagnosis of dementia other than probable AD.
- Comorbidity that precludes study participation or data interpretation.
- Any psychiatric disorder that would interfere with compliance in the study.
- Any severe somatic illness that would interfere with compliance and participation in the study.
- Use of high dose vitamin B3 supplementation within 30 days of enrolment.
- Metabolic, neoplastic, or other physically or mentally debilitating disorder at baseline visit.
- Current treatment with Oral Anticoagulation Therapies
- Implants that preclude MRI examinations, e.g. DBS, pacemaker

# **5 TREATMENT**

For this study NR (Niagen®, Chromadex) is defined as the Investigational Product(s) (IP). IP includes also active comparator and placebo.

# 5.1 Drug Identity, Supply and Storage

NR (Niagen®, Chromadex) and placebo will be manufactured and provided from Chromadex. Both NR and Placebo will be prepared as identical capsules. The drug has marketing consent in Norway but is not registered by Statens legemiddelverk (SLV)/Direktoratet for medisinske produkter (DMP) as a medical drug, but as a supplement. The NR and placebo have a 1-year expiry date. Both the NR and placebo will be stored in room temperature with temperature <25 degrees (according to instructions given by Chromadex).

# 5.2 Dosage and Drug Administration

Each NR capsule contains 250mg.. To keep the study fully blinded, all participants will receive the same number of daily capsules irrespective of which treatment group they belong to. To achieve this, NR capsules will be combined with placebo capsules as necessary (see below):

- Patients in the NR 1000mg group will administer orally [2 NR capsules (500mg) + 4 placebo capsules] x 2 times daily (1000mg NR daily in total).
- Patients in the NR dose escalation group will administer orally the following doses:
  - Weeks 0-4: [2 NR capsule (500mg) + 4 placebo capsules] x 2 times daily (1000mg NR daily in total).
  - Weeks 5-8: [4 NR capsule (1000mg) + 2 placebo capsule] x 2 times daily (2000mg daily total).
  - Weeks 9-12: [6 NR capsules (1500mg) + 0 placebo capsule] x 2 times daily (3000mg daily total).
- The placebo group will administer orally [6 placebo capsules] x 2 times daily.

There is no specified time of day the dosages should be taken, only that they should be taken with about 12 hours apart, if possible. If a dose is missed, the patient can take the missed dose as soon as it is remembered, provided it is shorter time to the missed dose than the next scheduled dose. There are no restrictions with respect to combining the dose with other medication and/or food. The study medication is to be taken every day during the treatment period, including prior to study visits.

# 5.3 Duration of Therapy

Therapy duration for the study is 3 months (12 weeks).

# 5.4 Cognitive Therapy During Screening and IP treatment period

Eligible and consenting men and women with AD may use standard treatments with Cholinesterase inhibitors and memantine can be used if stable for 8 weeks prior to

screening and baseline visits. The treatment regime will then be frozen and remain unchanged for the study period (3 months). At the end of study visit (month 3), the physician determines (yes/no) whether the patient is still adequately treated for his/her AD with their current standard treatment.

#### 5.5 Concomitant Medication

There are no restrictions on any other use of medications. All patients should use medications prescribed prior to enrollment in the study. There are no restrictions with respect to starting new medications that are necessary for the patient.

The Patient should not take any vitamin B3 supplements for the duration of the study.

All concomitant medication (incl. vitamins with the exception of vitamin B3, herbal preparation and other "over-the-counter" drugs) used by the patient will be recorded in the patient's file and CRF.

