# Screening checklist:

- 1. Patient signed informed consent for N-DOSE AD
- 2. Patient signs informed consent for consent for storage and analysis of biological material ("Samtykke for lagring av biologisk material i biobank for demens og aldring")
- 3. Physical examination (general neurological examination) at first screening
- 4. MoCA
- 5. Clinical AD diagnosis Criteria
- 6. Record current use of medication. Advise to stop any use of vit B3 supplements
- 7. Plan/conduct Lumbar puncture to verify AD diagnosis
- 8. If the patient is ready for enrollment, they are referred to baseline study visit (including MRI and PET).
- 9. The study partner is given the 3-day dietary registration form along with instructions on how to fill it out and deliver to the study nurse at baseline.
- 10. Give instructions on how to collect urine and fecal sample before the baseline visit.

# 6.2.2 Baseline/Week 0

- At the first study visit the investigator needs to verify the informed consent for the study and offer the subject to sign the informed consent for storage and analysis of biological material (Samtykke for lagring av biologisk materiale i FORSKNINGSBIOBANKEN FOR ALDRING, DEMENS OG NEVROLOGI).
- 2. Investigator verifies anamnestic information gathered at screening, current use of medication and medical history.
- 3. Investigator verifies fulfillment of inclusion and exclusion criteria.
- 4. The study identification number is assigned (see section 5.9).
- 5. Study medication is dispensed to the subject by the study nurse and the patient is reminded to take the study medication every day including at the morning of each visit.
- 6. The following clinical examination are performed by the study nurse or investigator (see flowchart in section 6.1):
  - a. Vital signs
  - b. Hight, body weight and BMI
  - c. MoCA
  - d. ADAS-COG
  - e. CDR
  - f. Trail Making Test (TMT)
  - g. MADRS
  - h. NPI-Q
  - i. IADL and PADL
- 7. Routine blood tests are done (see flowchart in section 6.1)
- 8. Samples for biobanking are taken (see flowchart in section 6.1):
  - a. EDTA whole blood
  - b. Snap-frozen whole blood
  - c. PAXgene blood for RNA
  - d. Platelets

- e. Serum
- f. Fecal sample
- g. Urine sample
- 9. Imaging is conducted
  - a. 31P-MRS & 1H-MRS
  - b. FDG-PET

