3.4.2 Protocol Deviations

The following are pre-defined major protocol deviations regarded to affect the efficacy of the intervention:

- Entering the trial when the eligibility criteria should have prevented trial entry.
- Discontinuation of intervention prior to 84 ± 7 days.
- Major change in concomitant choline-esterase or memantine treatment.
- Received or used other intervention than allocated.
- Adherence to allocated treatment below 80%.

- Visit date interval larger than 28 ± 7 days between individual visits (i.e.: V1 and V2, V2 and V3, and V3 and V4).
- Visit date interval larger than 84 ± 7 days from V1 to V4.
- Not fasting before neuroimaging with blood glucose > 8

Protocol deviations are classified prior to unblinding of treatment. The number (and percentage) of patients with major and minor protocol deviations will be summarized by treatment group with details of type of deviation provided. The patients that are included in the FAS analysis data set (see point 3.5 below) will be used as the denominator to calculate the percentages. No formal statistical testing will be undertaken.

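### Protocol 5.5 prohibits vitamin B3 supplements but leaves them out of the concomitant-medication record, so detecting such use, and removing users from the per-protocol set, is left to chance

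*Protocol*

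**What the plan says.** - **Prohibition.** Protocol 5.5: "The Patient should not take any vitamin B3 supplements for the duration of the study". No dose threshold is attached.
- **Recording.** The following sentence of 5.5 defines what goes into the patient's file and CRF: "All concomitant medication (incl. vitamins with the exception of vitamin B3, herbal preparation and other", and then over-the-counter products.
- **Entry.** Protocol 4.4 excludes only "Use of high dose vitamin B3 supplementation within 30 days of enrolment". The screening checklist in Protocol 6.2.1 tells staff: "Record current use of medication. Advise to stop any use of vit B3 supplements".
- **Availability of the product.** Protocol 5.1: "The drug has marketing consent in Norway but is not registered by" the national agency "as a medical drug, but as a supplement". Protocol 1.1.2 describes NR as a form of vitamin B3.
- **Deviation lists.** Protocol 10.3 and SAP 3.4.2 both contain "Received or used other intervention than allocated". Neither names vitamin B3 or NAD precursors. The SAP list does name another co-medication: "Major change in concomitant choline-esterase or memantine treatment".
- **Use of the sets.** The PPS drops patients with major deviations. SAP 5.1.6 makes the FAS versus PPS comparison the sensitivity analysis for the primary endpoint.

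**The concern.** Of all off-trial products, a B3 supplement is the one that works through the same pathway as the intervention and moves the outcome being measured. The footnote in Protocol 10.3 says that NAD levels plateau within 1 to 2 weeks of NR treatment, so use begun shortly before the week-12 scan could be enough to matter.

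A site that applies 5.5 as written will log multivitamins and herbal products but not this class. If use is not captured, it cannot be classified as a deviation, and the user stays in the PPS, the set meant to be free of such use. Agreement between FAS and PPS would then say little about contamination. A small difference between the dose-escalation (DE) and dose-stable (DS) groups could be read as weak dose-response when part of it came from supplement use in the DS group.

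**Working it through.** **1. Is there another route that captures B3 use?**

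- *Concomitant-medication row of the flow chart (Protocol 6.1).* Completed at screening and at V1 to V4, but its content is governed by 5.5 and so inherits the exception.
- *Screening checklist and baseline verification (Protocol 6.2.1, 6.2.2).* These cover current medication before treatment starts, not use between V1 and V4.
- *Adherence (SAP 3.4.1).* Counts study capsules only.
- *Dietary record.* The flow chart shows it at V1 and V4. Protocol 6.2.3 repeats baseline points that include handing out the form, so it may also be collected at other visits. Nothing says that it asks about supplements.
- *Blood and urine NAD metabolome (SAP 4.4).* Measured at V1 to V4 as an exploratory endpoint, with no rule for using it to detect outside B3.
- *General deviation rule (Protocol 11.2).* Significant deviations go in the CRF, but only once someone has learned of them.

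Several routes could reveal use. None prompts for it.

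**2. Which contrast moves, and in which direction?**

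Inputs from Protocol 10.1 and SAP 5.5: 1000 mg raises cerebral NAD by a factor of 1.27 (+27 points), placebo changes by -0.43%, and the response is linear in dose. The arms are 20 placebo (PL), 20 DS and 40 DE.

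- 3000 mg: 3 × 27 = +81 points.
- DE-DS at week 12: 81 - 27 = 54 points.
- DS-PL: 27 + 0.43, about 27 points.

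If *k* of *n* patients in an arm each add 27 points (an assumed extra 1000 mg/day of a precursor with the same effect as NR), the arm mean shifts by 27*k*/*n*.

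| Assumed use | Shift in arm mean | DE-DS | DS-PL |
|---|---|---|---|
| None | 0 | 54 | 27 |
| 2 of 20 in DS | +2.7 | 51.3 (-5%) | 29.7 (+10%) |
| 4 of 20 in DS | +5.4 | 48.6 (-10%) | 32.4 (+20%) |
| 2 of 20 in PL | +2.7 | 54 | 24.3 (-10%) |
| 4 of 20 in PL | +5.4 | 54 | 21.6 (-20%) |
| 20% of every arm | +5.4 each | 54 | 27 |

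If the response saturates, the linear rows no longer apply, and even equal use could narrow DE-DS.

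**3. What might this do to power?**

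The plan's 30 in the DE group cannot be reproduced, because no SD is stated. The point does not rest on that figure. For scale only, take the standardised difference that gives 90% power (two-sided 5%, normal approximation) with DS 15 and DE 30:

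*d* = (1.960 + 1.282) × √(1/15 + 1/30) = 1.025, which means SD = 0.54/1.025 = 0.527.

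If the contrast shrinks by a fraction *c*, power = Φ(*d*(1 - *c*)/√(1/n_DS + 1/n_DE) - 1.960):

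| Reduction in DE-DS | DS 15 / DE 30 | DS 20 / DE 40 |
|---|---|---|
| 0 | 90.0% | 96.3% |
| 5% | 86.9% | 94.5% |
| 10% | 83.1% | 92.1% |

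With equal use by 20% of each arm, the difference stays at 54 points and the SD becomes √(0.527² + 0.2 × 0.8 × 0.27²) = 0.538. Power at 15/30 is then about 89%.

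**The case against.** The best reply is that the safeguards already exist in general form. Taking B3 breaches 5.5, and significant deviations must be recorded. Self-use of NR fits naturally under "Received or used other intervention than allocated". Deviations are classified before unblinding. According to Protocol 1.1.3, all NR recipients in the Parkinson's pilot trial showed a clear metabolic response in blood, so a placebo patient taking NR would probably leave a trace in samples already planned. The exception may also be a drafting slip, meant to say that B3 is excepted from the *permitted* vitamins. The PPS is only a sensitivity set, and blinding gives no obvious reason for use to concentrate in one arm.

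Much of this stands, and it rules out stronger readings that a reader might infer:

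- *That use would go unseen.* The routes above could reveal it.
- *That a user in DS or placebo shrinks both contrasts.* A DS user narrows DE-DS but widens DS-PL. A placebo user narrows DS-PL and leaves the primary contrast alone.
- *That a user has in effect switched arm.* A DS patient adding 1000 mg/day would be at 2000 mg, not the 3000 mg that DE receives by week 12.
- *That dilution is to be expected.* Under linearity, equal use across arms leaves the mean DE-DS difference unchanged.

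What the reply does not supply is a step that asks the question or assigns the metabolite data to answer it. The generic deviation item works only for use that has come to light. If the sentence is a slip, it still instructs sites not to record, which is a reason to correct it.

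**Conclusion.** The point holds as a data-capture defect with a modest, conditional effect on the analysis. The two sentences of 5.5 pull apart, neither deviation list names the one prohibited supplement class, and the PPS therefore cannot be relied on to exclude users.

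The documents give no rate of B3 use, so the bias cannot be sized. The 5 to 10% loss in DE-DS assumes that 2 to 4 of 20 DS patients and no DE patients take a precursor worth 27 points, with a linear response. The matching power figures also rest on an SD chosen to fit the plan's 90%. The primary FAS analysis remains valid as a comparison of randomised groups. What is weakened is the ability to tell a small true dose effect from one narrowed by outside supplementation.

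**What to change.** - **Protocol 5.5.** Reconcile the two sentences by deleting the recording exception. Record any vitamin B3 or NAD-precursor product (NR, NMN, nicotinamide, niacin) with dose and start and stop dates, asked of patient and study partner at V1 to V4 on the existing concomitant-medication form. The prohibition itself is not altered.
- **Protocol 10.3 and SAP 3.4.2.** Add use of such a product between V1 and V4 as a named major deviation for the PPS, classified before unblinding. Keep these patients in the FAS.
- **If visits are already complete.** The SAP line can still be added before unblinding, together with a query of source notes for recorded B3 use.

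Cost: one sentence, one line in each list and one question on an existing form. The downside is that a few patients may leave the PPS.

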# 5.6 Subject Compliance

Patient compliance will be determined based on self-report at study visits (using information from the study participant and study partner). A pill count of remaining medication will be performed when providing new study medication and at the end of the study.

# 5.7 Drug Accountability

The responsible site personnel will confirm receipt of study drug and will use the study drug only within the framework of this clinical study and in accordance with this protocol. Receipt, distribution, return, and destruction (if any) of the study drug must be properly documented according to the sponsor's agreed and specified procedures.

Study drugs are stored locally at the study site and distributed by the study nurse upon registration in CRF. Remaining study drug is returned for pill count.

# 5.8 Drug Labeling

The investigational product will have a label permanently affixed to the outside and will be labeled according with ICH GCP and national regulations, stating that the material is for clinical trial / investigational use only and should be kept out of reach of children.

Label will include:

- Patient's initials
- Study number (CRF number)
- Date dispensed

# 5.9 Subject Numbering

At the screening visit, patients will be sequentially allocated a patient study number. The subject will be identified by this patient study number for the remainder of the study. Once a patient number has been assigned, no attempt will be made to use that number again.

The patient study number will be in the following format: XX-YYY where XX is the study site number and YYY is the patient id number. If a patient number is allocated incorrectly, no attempt will be made to remedy the error once study treatment has been dispensed. Any replacement patients will be given the next patient number in the sequence.

# **6 STUDY PROCEDURES**

# **6.1 Flow Chart**

Table 1. Trial flow chart

	Screening Period		Treatment Period  Study Visit:			End of study visit
Event	First Screening	Next/Last screening 	Visit-1 Baseline 	Visit-2	Visit-3	Visit-4
Time			Week 0	Week 4	Week 8	Week 12
Informed consent	Х					
Informed consent biobank, optional	Х					
AD Clinical diagnosis Criteria	Х		Х			
Inclusion/exclusionEvaluation	х		Х			
Medical history 	х		Х			
Neurologic exam 	х		Х	Х	х	Х
Physical Examination 	Х		Х	Х	Х	Х
Body height			Х			
Body weight and BMI			Х	Х	Х	Х
Vital signs 			Х	Х	Х	Х
Record of concomitant medication	Х		Х	Х	Х	х
MoCA 	Х		Х	Х	Х	Х
CDR 	Х		Х	Х	Х	Х
ADAS-COG 13			Х	Х	х	Х
Trail Making Test (TMT) 	Х		Х	Х	Х	Х
31P-MRS, 1H-MRSand FDG- PET imaging			Х	х	Х	х
MADRS 	Х		Х	Х	Х	Х
NPI-Q, and IADL and PADL 	Х		Х	X	Х	Х
Dietary registration (3 days prior to visit)			Х			х
Routine blood tests 			Х	Х	Х	Х
hCG 	Х					

Blood for biobanking 		Х	Х	Х	Х
Cerebrospinal fluid collection 	Х				Х
Fecal sample collection		Х			Х
Urine sample collection		Х	Х	Х	Х
Treatment (IP) dispensation 		Х	Х	Х	
Cognitive treatment stable 		Х			Х
Adverse event			Х	Х	Х

Superscripts refer to the specifications below.

#### **Specifications**

- Medical history includes: family history of neurological illness (what and who), family history of dementia (what and who), smoking history (period, pack-years), first AD symptoms, months since first AD symptoms,.
-  General Neurological examination
- 3. Heart and lung auscultation, abdominal palpation, any other examination dictated by patient's condition/symptoms
- 4. Blood pressure, pulse, temperature
- 5. Not repeated at baseline if conducted at screening within 4 weeks prior to the baseline visit.
-  CRP, ALAT, ASAT, GT, bilirubin, ALP, creatinine, urea, RBC, Hb, WBC with differential, platelets, CK, FT4, TSH, B12, folic acid, homocysteine, methylmalonic acid, sodium, potassium, glucose.
- Women of childbearing potential will also have a pregnancy test performed.
- EDTA blood, snap-frozen EDTA blood, PAXgene, platelet isolation, serum (see lab manual for details).
- 9. CSF, including Amloid-β and Tau protein levels to verify the AD diagnosis.
- 10. To ensure correct dosages during dose escalation and if necessary to resupply.
- 11. The patient has to be stable if on a standard cognitive treatment for 8 weeks prior to baseline. There should not be more than 3 months from last screening to baseline visit.

# 6.2 By Visit

# 6.2.1 Screening Visits/ Before start of Investigational Product (IP)

The first screening visit aims to determine if the patient is eligible to be included in the study. A full physical examination, anamnestic medical history, cognitive testing and lumbar puncture to establish AD pathology is performed. If the patient fulfills the inclusion/exclusion criteria and gives informed consent, standard treatment with cholinesterase inhibitors and memantine must be stable for 8 weeks prior to screening and baseline visits.

If the patient fulfills the inclusion/exclusion criteria, the patient is called in for the baseline study visit (week 0 study visit). The Baseline study visit should be within 8 weeks from the time the lumbar puncture was performed. There should not be more than 3 months from last screening to baseline visit.

# Screening checklist:

- 1. Patient signed informed consent for N-DOSE AD
- 2. Patient signs informed consent for consent for storage and analysis of biological material ("Samtykke for lagring av biologisk material i biobank for demens og aldring")
- 3. Physical examination (general neurological examination) at first screening
- 4. MoCA
- 5. Clinical AD diagnosis Criteria
- 6. Record current use of medication. Advise to stop any use of vit B3 supplements
- 7. Plan/conduct Lumbar puncture to verify AD diagnosis
- 8. If the patient is ready for enrollment, they are referred to baseline study visit (including MRI and PET).
- 9. The study partner is given the 3-day dietary registration form along with instructions on how to fill it out and deliver to the study nurse at baseline.
- 10. Give instructions on how to collect urine and fecal sample before the baseline visit.

# 6.2.2 Baseline/Week 0

- At the first study visit the investigator needs to verify the informed consent for the study and offer the subject to sign the informed consent for storage and analysis of biological material (Samtykke for lagring av biologisk materiale i FORSKNINGSBIOBANKEN FOR ALDRING, DEMENS OG NEVROLOGI).
- 2. Investigator verifies anamnestic information gathered at screening, current use of medication and medical history.
- 3. Investigator verifies fulfillment of inclusion and exclusion criteria.
- 4. The study identification number is assigned (see section 5.9).
- 5. Study medication is dispensed to the subject by the study nurse and the patient is reminded to take the study medication every day including at the morning of each visit.
- 6. The following clinical examination are performed by the study nurse or investigator (see flowchart in section 6.1):
  - a. Vital signs
  - b. Hight, body weight and BMI
  - c. MoCA
  - d. ADAS-COG
  - e. CDR
  - f. Trail Making Test (TMT)
  - g. MADRS
  - h. NPI-Q
  - i. IADL and PADL
- 7. Routine blood tests are done (see flowchart in section 6.1)
- 8. Samples for biobanking are taken (see flowchart in section 6.1):
  - a. EDTA whole blood
  - b. Snap-frozen whole blood
  - c. PAXgene blood for RNA
  - d. Platelets

- e. Serum
- f. Fecal sample
- g. Urine sample
- 9. Imaging is conducted
  - a. 31P-MRS & 1H-MRS
  - b. FDG-PET
- 10. All data gathered during study visits is either written into the electronic journal or filled out in paper format with appropriate date and signatures. Each patient will have their own folder with gathered clinical data. The clinical tests are recorded in paper format.
- 11. The patient's study partner is given the 3-day dietary registration form along with instructions on how to fill it out and deliver to the study nurse at the next visit.
- 12. The patient and study partner is instructed to take the study medication every day for the remainder of the study. The study medication or placebo is to be taken as outlined in section 5.2. The capsules are taken in the morning and evening. There is no specified time of day the dosages should be taken, only that they should be taken with about 12 hours apart if possible. If a dose is missed, the patient can take the missed dose as soon as it is remembered, provided it is shorter time to the missed dose than the next scheduled dose. There are no restrictions with respect to combining the dose with other medication and/or food.

